via EtCO₂. Masks B & C both had higher rate of total leaks due to higher rate of unintentional leaks which may improved CO₂ wash out, hence, led to no differences in PtcCO₂.⁸ Another study compared total face mask against oronasal mask impact on gas exchange (PvCO₂) favors total face mask in the first 6 hours and during the acute phase of respiratory failure using NIPPV.⁷ Both Medrinal and Sadeghi assessed gas exchange not masks' CO₂ clearance. Since the intentional leak impacts CO₂ clearance, and the intentional leak level depends on the level of pressure.⁸ The previous studies didn't study different level of EPAP (baseline pressure). One level of EPAP pressure of 4 cm H₂O was used in Medrinal study based on Samolski's finding.⁸ While in Sadeghi's study, IPAP started at 10 cm H₂O and EPAP started at 4 cm H₂O. IPAP and EPAP were increased gradually based on subjects' need, therefore it lacked consistency in EPAP level.⁹

ICU ventilators using double limb circuit is an alternative to deliver NIPPV, however, researches on minimum baseline pressure required to prevent CO₂ rebreathing is not clear as well. In a study that compared 3 types of masks (2 ONM and 1 FFM) to helmet in acute hypercapnia respiratory failure. NIPPV in both group improved arterial blood gases. ICU ventilators settings in masks group used positive end expiratory pressure (PEEP) referring to baseline pressure that ranged from 3 – 5 cm H₂O (mean 4.26 ± 1.92); and inspiratory pressure adjusted to achieve tidal volume of 6-8 ml/kg (16.37 ± 4.19). On the other hand, settings for helmet groups were ~ 30%.¹¹

The answer regarding effective EPAP level to wash out CO₂ remains uncertain. The purpose of this study is to compare the efficacy of CO₂ clearance between different NIPPV interfaces (oronasal and full face masks) when using double limb circuit ICU

ventilator at lower levels of EPAP. The aim of this study is to determine the EPAP (baseline pressure) required to effectively wash out CO₂ for each mask and assess perceived level of comfort with each mask.

3- Methods:

This study will be a randomized crossover trial that will be conducted at Rush University.

Normal volunteers will be recruited from Rush University Medical Centers. Volunteers will be screened with inclusion and exclusion criteria and an informed consent is required in order for them to participate. Demographic (age, gender, ethnicity) will be obtained.

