Also, initial baseline vital signs (heart rate, blood pressure, respiratory rate, and oxygen saturation) will be obtained. EtCO₂ will be obtained at baseline and periodically using an oral/nasal sample line with the CapnostreamTM 20p monitor (Medtronic, Minneapolis, MN). The study will use a double limb circuit ICU ventilator Puritan BennettTM (Medtronic, Dublin, Ireland).

We will evaluate 4 NIPPV masks (2 oronasal masks and 2 full face masks).

[figure not shown]
Oronasal masks will be labeled as group A and numbered as A1 and A2; while full face masks will be labeled group B and numbered as B1 and B2. Order of the masks will be randomly chosen in two steps. First steps will be choosing A or B then randomly assign mask in each of these groups. We will randomly assign mask in group A or B by drawing an initial mask from the group and then continue the sequence of masks from that point.

For example, we randomly chose group A, then randomly chose A2, the sequence will be A2, A1. Then we would randomly choose B2, then the sequence would be B2, B1.

All subjects will perform 15 minutes on each mask followed by 5 minutes wash out interval between masks. EPAP levels will be 0, 2, 4, & 5 while IPAP remains at 5 higher than EPAP. EtCO₂ will be collected at 4:00, 4:30 and 5:00 minute mark. These three measures should differ by less than 20% of their average. Also, subjective mask

comfort will be assessed via visual analog scale (VAS) with 1 referring to least comfortable and 5 being the most comfortable after 5 each EPAP setting.

Procedure figure:

4- Subject Population:

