4.4.2. Facial surgery or deformity

4.4.3. Ear infection

4.4.4. History of pulmonary or cardiac disease

5- Research recruitment and Consent Procedures:

5.1. Subjects will be recruited from students enrolled, faculty, and staff at Rush University.

5.2. An informed consent will be obtained by the investigators for all eligible candidate that meet the criteria.

6- Compensation:

Volunteers will be compensated with \$ 25 Visa gift card

7- Special precautions:

- 7.1. Subjects refrain from eating at least 60 min before the study
- 7.2. Study will be stopped if HR change by 20% from baseline for more than 1 min.
- 7.3. Study will be stopped if subjects complain of shortness of breath

8- Confidentiality:

Subject names, date of birth, and contact information (email) will be stored in REDCap. However, only de-identified data will be used for analysis.

9- Data Collection Instruments/ Data Collection Procedures/Data Analysis Plan:

Data for each subject will be recorded in REDCap

10- Variables:

Dependent: CO₂ clearance, level of comfort-

Independent: NIPPV interface, level of EPAP

11- Limitation:

It is performed on healthy subjects.

12- Analysis:

Data will be recorded in REDCap. Demographics data age (interval), gender (nominal),

ethnicity (nominal) will be collected. HR (continuous), RR (continuous), SpO2

(continuous), ETCO₂ (continuous), EPAP (ordinal), IPAP (ordinal) will be collected.

Means and Standard deviations will be calculated for aforementioned data. NIPPV interfaces number, sizes will be collected. Level of comfort will be collected; median and interquartile ranges will be calculated. Relationship between dependent variable ETCO₂ and independent variable EPAP level will be analyzed by a Kruskal-Wallis test to determine if a significant difference exists. If a significant difference is found a Mann-Whitney U Test will be used to determine which EPAP levels significantly differ. Relationship between dependent variable comfort level and independent variable NIPPV interfaces will be analyzed a Kruskal-Wallis test to determine if a significant difference exists. If a significant difference is found a Mann-Whitney U Test will be used to determine which masks were significantly more comfortable.

Literature cited:

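### Section 12 plans no within-volunteer EtCO₂ difference, no confidence interval and no EtCO₂ comparison between masks, although the crossover design and the aims call for all three

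*Combined protocol and SAP*

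**What the plan says.** The design is stated in Section 3 (Methods): "This study will be a randomized crossover trial that will be conducted at Rush University". Exposure is complete within each person: "All subjects will perform 15 minutes on each mask followed by 5 minutes wash out interval between masks". The settings are fixed in the same section: "EPAP levels will be 0, 2, 4, & 5 while IPAP remains at 5 higher than EPAP". Three EtCO₂ readings are taken per setting, but no rule says how they are combined.

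The Introduction closes with two aims for CO₂: to compare clearance between oronasal and full face masks, and to find, for each mask, the EPAP that clears CO₂ effectively.

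Section 12 lists age, gender, ethnicity and vital signs, and then "ETCO₂ (continuous), EPAP (ordinal), IPAP (ordinal) will be collected". The next sentence is "Means and Standard deviations will be calculated for aforementioned data". Comfort has its own rule: "Level of comfort will be collected; median and interquartile ranges will be calculated". EtCO₂ is then related to EPAP level by a Kruskal-Wallis test, with Mann-Whitney tests to locate differences if the first test is significant. The only test in Section 12 that compares masks is for comfort.

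**The concern.** The question is one of magnitude: how much does EtCO₂ change between EPAP levels in a given mask, and between masks at a given level? The planned tests are described only as showing whether, and between which levels, a significant difference exists. A p-value does not say how many mmHg separate two levels. A non-significant result in 20 volunteers does not show that two levels clear CO₂ equally well, and an interval is what would show how large a difference remains possible.

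The comparison of masks on CO₂ clearance, a stated purpose, has no EtCO₂ analysis at all. The comparison of EPAP levels separately for each mask is not set out either.

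The planned SDs cannot fill the gap. In a crossover, the error of a difference depends on how strongly two measurements in the same person are correlated. No planned output carries that information.

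**Working it through.** **The plan's own figure.** The only quantity given is a sample size of 20 (Section 4.2). The documents give no alpha, power, effect size, SD or correlation behind it, so there is no calculation to reproduce.

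**What each planned EtCO₂ output provides**

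| Planned output | Gives a difference? | Gives its precision? |
|---|---|---|
| Means and SDs, grouping unstated | By subtraction, if given by condition | No |
| Kruskal-Wallis across EPAP levels | No | No |
| Mann-Whitney, if the first test is significant | Not as described | No |
| EtCO₂ between masks | Not planned | Not planned |

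**Can precision be recovered from the SDs?**

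Inputs:
- n = 20 (Section 4.2).
- One value per volunteer per condition, taken as the average of the three readings (assumption).
- Common SD s in the two conditions being compared (assumption; 4 mmHg for illustration, range 3 to 5).
- Within-volunteer correlation r between the two conditions (assumption; range 0 to 0.9).

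Formulas:
- SD of paired differences = s × sqrt(2(1−r)).
- Paired 95% half-width = t(0.975, 19) × s × sqrt(2(1−r)/20), with t = 2.093.
- Half-width if the two SDs are treated as independent = t(0.975, 38) × s × sqrt(2/20), with t = 2.024.
- Ratio of standard errors, independent to paired = 1/sqrt(1−r).

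| r | SD of differences / s | SE ratio | Paired half-width, s = 4 | Independent half-width, s = 4 |
|---|---|---|---|---|
| 0 | 1.41 | 1.00 | 2.65 | 2.56 |
| 0.3 | 1.18 | 1.20 | 2.22 | 2.56 |
| 0.5 | 1.00 | 1.41 | 1.87 | 2.56 |
| 0.7 | 0.77 | 1.83 | 1.45 | 2.56 |
| 0.8 | 0.63 | 2.24 | 1.18 | 2.56 |
| 0.9 | 0.45 | 3.16 | 0.84 | 2.56 |

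At r = 0.8: paired, 2.093 × 4 × sqrt(0.4/20) = 1.18 mmHg; independent, 2.024 × 4 × sqrt(2/20) = 2.56 mmHg. With s from 3 to 5 and r = 0.8, the paired half-width runs from 0.89 to 1.48 mmHg. The independent figure is 0.640 × s, so 1.92 to 3.20 mmHg.

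The last column does not move with r. The same published SDs are therefore compatible with any paired half-width from 0.84 to 2.65 mmHg over this range of r. At r = 0 the paired interval is slightly the wider of the two, because it has 19 degrees of freedom rather than 38.

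These figures describe a contrast of two conditions within one mask. A contrast of EPAP levels averaged over masks follows the same formulas, with s and r taken for each volunteer's averaged values, which the documents also do not give.

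**The nominal and fixed variables.** Taken at its word, the means-and-SDs sentence also covers gender and ethnicity, which Section 12 itself labels nominal. The mean of a nominal variable depends only on its coding: a 10/10 gender split gives 0.5 coded 0/1 and 1.5 coded 1/2. It also covers EPAP and IPAP. If all four levels are delivered equally, the EPAP mean is (0 + 2 + 4 + 5)/4 = 2.75 and the IPAP mean is 7.75, each with SD 1.92 to 1.93 over 80 or 320 records, whatever the volunteers do.

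**The case against.** **Differences are not wholly lost.** In a complete crossover, the mean within-volunteer difference equals the difference of the two condition means. If the report gives EtCO₂ by condition, the size in mmHg follows by subtraction. This stands. A reader might infer that the trial can give no size in mmHg at all, but the plan leaves the grouping open, so the documents do not support that. What is missing is a planned difference and, on any grouping, its precision.

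**Nobody plans to use the SDs as error bars.** This also stands. Section 12 proposes no standard errors or error bars, so the inflation factor is not an error the trial will make. It shows only that the planned output cannot be converted into an interval. Nor do the documents show that the SDs are mostly between-volunteer spread. That is plausible, but no SD or correlation is given.

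**The nominal means are a drafting slip.** Agreed. The scale of each variable is correctly labelled, the sentence may have been meant only for the list just before it, and no conclusion changes. A reader might infer that one faulty descriptive rule spoils the results. It does not: comfort has its own median and interquartile range rule, and means and SDs are proper for age, HR, RR, SpO₂ and EtCO₂.

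**The point overlaps with the use of unpaired tests on crossover data.** Partly so. A repeated-measures model would normally supply differences and intervals. Simply replacing the rank tests with paired ones would not, so the point remains separate.

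**Completeness is not assured.** Four EPAP levels at five minutes each would take 20 minutes, against 15 per mask in Section 3. Those passages must be reconciled. Stopping under Sections 7.2 and 7.3 could also remove conditions for some volunteers. Subtracted condition means would then no longer equal the mean paired difference, which makes a planned paired estimate more useful.

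**Conclusion.** The point holds as a gap in estimation. For its main outcome, this crossover trial plans no within-volunteer difference and no confidence interval, and it plans no EtCO₂ comparison between masks although that is a stated purpose. If the planned SDs are treated as independent, the standard error of a difference is overstated 1.4-fold at r = 0.5 and 2.2-fold at r = 0.8. With s = 4 mmHg and r = 0.8, the half-width is 2.56 instead of 1.18 mmHg. Both s and r are assumptions. The direction needs only an appreciable positive r, which is plausible for repeated EtCO₂ in the same person.

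The change should be made before analysis. The means for gender, ethnicity, EPAP and IPAP are a minor drafting matter and carry none of this weight.

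**What to change.** Change Section 12 as follows.

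1. Average the three readings to one EtCO₂ value per volunteer and condition, and report mean and SD for each mask-by-EPAP condition.
2. Report mean within-volunteer EtCO₂ differences with 95% confidence intervals between EPAP levels (within each mask and averaged over masks) and between masks, whether or not the overall test is significant.
3. State that these intervals are unadjusted, or name the multiplicity adjustment. Four levels give 6 pairs: 6 × 4 = 24 within masks and 6 averaged over masks. Four masks give 6 more when averaged over EPAP levels, so 36 in all.
4. As a drafting correction only, give gender and ethnicity as n (%), and treat EPAP and IPAP as design factors, with delivered settings listed only as a check.

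The cost is a few sentences, a longer results table and several contrasts to interpret. No new data are needed.

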Student Research Project Proposal

Title:

Carbon Dioxide (CO₂) Clearance from various face masks in Normal Volunteers at various level of Expiratory Positive Airway Pressure (EPAP) when Using a Non-Invasive Positive Pressure Ventilation (NIPPV)

Investigators:

Mentor:

[name], MHS, RRT, FAARC, FCCP

Graduate Student:

[name], Respiratory Care Department, Rush University.

Study aim:

Determine the EPAP (baseline pressure) required to effectively wash out CO₂ for current available masks, and assess perceived level of comfort with each mask with using noninvasive ventilator.

1- Abstract:

Background: Noninvasive positive pressure ventilation (NIPPV) can be delivered via single limb circuit or double limb circuit ventilators. There are many advantages to NPPV. However, a reasonable number of questions remain unanswered, such as mask impact on carbon dioxide (CO₂) clearance based on EPAP level.

Objective: Determine the EPAP (baseline pressure) required to effectively wash out CO₂ for each mask, and assess perceived level of comfort with each mask with ICU ventilator.

Method: This study will be a randomized crossover trial that will be conducted at Rush University. The study will be conducted with 20 healthy volunteers who will be placed on ICU ventilator operating in the NIPPV mode. All subjects will perform 15 minutes of breathing on NIPPV on each mask of the 4 different masks (2 oronasal and 2 full face masks) that are randomly selected. Breathing through each mask will be followed by a 5-minute wash out period between masks. End tidal Carbon Dioxide (EtCO₂) will be sampled nasal/oral. Different levels of EPAP will be set and CO₂ clearance will be monitored. Additionally, subjective mask comfort will be assessed via visual analog scale (VAS) with 1 referring to least comfortable and 5 being the most comfortable.

2- Introduction

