4.2. Sample Size

20 healthy subjects.

4.3. Inclusion criteria:

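### Section 12 analyses a within-subject crossover with independent-samples tests (Kruskal-Wallis, Mann-Whitney) and does not define the unit of analysis; with one value per subject per level this makes the tests conservative and can cost substantial power

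*Combined protocol and SAP*

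**What the plan says.** **Design.** Section 3 (Methods) states: "This study will be a randomized crossover trial that will be conducted at Rush University". It continues: "All subjects will perform 15 minutes on each mask followed by 5 minutes wash out interval between masks". The Abstract agrees: "All subjects will perform 15 minutes of breathing on NIPPV on each mask of the 4 different masks". Section 4.2 gives the sample as "20 healthy subjects", with no SD, target difference, correlation or power.

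**Conditions and measurements (section 3).** "EPAP levels will be 0, 2, 4, & 5 while IPAP remains at 5 higher than EPAP". No allocation of subjects to EPAP levels is described, so the natural reading is that each subject receives all four. "EtCO₂ will be collected at 4:00, 4:30 and 5:00 minute mark". The next sentence asks that the three readings lie within 20% of their average. Comfort is scored from 1 to 5, with "5 being the most comfortable after 5 each EPAP setting", which yields several ratings per subject per mask.

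**Analysis (section 12).** For EtCO₂ the "independent variable EPAP level will be analyzed by a Kruskal-Wallis test to determine if a significant difference exists", with Mann-Whitney tests to locate differences. Comfort by mask gets the same two tests. No paired test, subject effect or mixed model appears anywhere. Section 12 does not say what one row of data is, whether EPAP levels are compared within each mask or over all masks together, or what alpha applies.

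**The concern.** Kruskal-Wallis and Mann-Whitney judge differences between levels against the full spread of the data, including stable differences between people. A crossover exists to remove that spread, because each person serves as his or her own control. Leaving it in the error term discards the advantage of the design.

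These tests are the only inferential analyses in the plan, and they carry both stated aims: the EPAP needed for each mask, and perceived comfort. If the tests are conservative, failure to separate EPAP levels could be read as a low EPAP clearing CO₂ as well as a higher one, when the test simply had little chance of showing a modest difference. If repeated values are entered as separate rows, the false-positive rate is no longer known.

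**Working it through.** **Inputs.** From the documents: 20 subjects, 4 masks, 4 EPAP levels, 3 EtCO₂ readings per setting. Assumed, because the documents give none: alpha 0.05, normal data with total SD 1, within-subject correlation ρ of 0.3 / 0.5 / 0.7 / 0.9. The stated sample size has no inputs, so it cannot be reproduced.

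**Step 1: one value per subject per level.** The variance of a difference between two level means is 2σ²(1 − ρ)/n; an independent-samples test takes it as 2σ²/n. Under the null, the Kruskal-Wallis statistic therefore behaves roughly as (1 − ρ) times a chi-square on 3 df. With critical value 7.81, type I error is about P(χ²₃ > 7.81/(1 − ρ)). The thresholds become 11.16 / 15.63 / 26.05 / 78.15, giving about 1.1 / 0.14 / 0.001 / 0%. This rough formula explains the direction. The figures relied on are simulated (20,000 data sets per setting for type I error and power; 10,000 per 0.05 SD step for the last two rows):

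| Assumed ρ | 0.3 | 0.5 | 0.7 | 0.9 |
|---|---|---|---|---|
| Type I error, Kruskal-Wallis | 1.2% | 0.3% | under 0.1% | 0% |
| Power, 0.4 SD at one level: Kruskal-Wallis | 13% | 8% | 4% | 1% |
| Power, 0.4 SD: Friedman | 23% | 31% | 49% | 94% |
| Power, 0.6 SD: Kruskal-Wallis | 36% | 30% | 25% | 20% |
| Power, 0.6 SD: Friedman | 47% | 63% | 86% | 100% |
| Power, 1.0 SD: Kruskal-Wallis | 89% | 91% | 93% | 96% |
| Power, 1.0 SD: Friedman | 92% | 98% | 100% | 100% |
| Shift for 80% power: Kruskal-Wallis | 0.90 SD | 0.89 SD | 0.88 SD | 0.86 SD |
| Shift for 80% power: Friedman | 0.85 SD | 0.72 SD | 0.56 SD | 0.32 SD |

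Friedman's type I error stays between 4.4% and 5.0%. For comfort as one 1-5 rating per mask (latent normal cut at −1, −0.3, 0.3 and 1; latent shift 0.6 SD; ρ 0.3 / 0.5 / 0.7), power is 33 / 29 / 22% with Kruskal-Wallis and 47 / 62 / 83% with Friedman.

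**Step 2: pooled rows.** If every reading is a row, each EPAP level has 20 × 4 × 3 = 240 values. Split a total variance of 1 into subject, subject-by-mask, subject-by-EPAP (v_SE), cell (v_C) and reading (v_R). Subject and subject-by-mask terms cancel between levels. What remains for a level mean is v_SE/20 + v_C/80 + v_R/240 = R/240, where R = 12v_SE + 3v_C + v_R. The test assumes 1/240. R well below 1 points to conservatism and R well above 1 to inflation. With only 20 subjects R is a rough guide, so simulated values are given beside it:

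- Subject 0.5, subject-by-mask 0.1, reading 0.4: R = 0.4; type I error 0.1% or less.
- Subject 0.8, v_SE 0.05, reading 0.15: R = 0.6 + 0.15 = 0.75; type I error about 4 to 4.5%, near nominal.
- Subject 0.5, subject-by-mask 0.1, v_SE 0.1, v_C 0.2, reading 0.1: R = 1.2 + 0.6 + 0.1 = 1.9; type I error about 28%. The same components give about 2% with readings averaged (20 × 4 = 80 values per level) and 0% with one mean per subject per level.

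Eighty averaged values per level can also exceed 5%: about 10% when v_SE is 0.2. Pooling all 80 comfort ratings per mask gave 0.2% to 25% over the component sets tried.

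**Step 3: pairwise tests.** Four levels give 4 × 3/2 = 6 pairs. With three equal levels and the fourth shifted by 2 SD, family-wise error among the equal levels is 5.9 / 2.5 / 0.4 / 0% under the planned sequence, 12-13% for Friedman plus unadjusted Wilcoxon, and 4.3-4.7% with Holm.

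**Step 4: complete blocks.** Four EPAP levels, each with a reading at 5:00, imply 4 × 5 = 20 minutes if the clock restarts at each level. Section 3 gives 15 minutes per mask. The procedure figure, not shown in the text available, may bear on this.

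**The case against.** **The error is on the safe side.** With one value per subject per level, a significant omnibus result is safer than its nominal level, and 1 SD shifts are found 89-96% of the time. At ρ = 0.3 the shift needed for 80% power moves only from 0.90 to 0.85 SD. All of this stands. The loss becomes serious at moderate or high correlation, and the documents give no reason to expect shifts near 1 SD.

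**The natural unit is the average.** The 20% agreement rule treats the three readings as replicates of one value. This stands as far as it goes: it makes 240 separate values the less natural reading, so the largest inflation figures should not drive the judgement. The rule does not make the average the analysis value, and nothing comparable exists for the comfort ratings.

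**Stronger readings a reader might infer.** One is that p-values are wrong whenever within-subject correlation is positive. That holds for one value per subject per level, but the second pooled case above is strongly correlated and still close to 5%. Another is that the unit alone sets the direction of the error. With pooled rows the variance components decide as well, and the documents give none. A third is that the pooled figures bound the possible error. They depend on the components chosen and are illustrations only.

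**Conclusion.** The concern holds. Section 12 applies independent-samples tests to within-subject comparisons: mask is within-subject by explicit statement, EPAP on the natural reading of section 3. With one value per subject per level, any positive correlation makes the planned tests conservative. For a 0.6 SD shift at one level the power given up against Friedman is about 11 points at ρ = 0.3 (47 − 36) and 61 points at ρ = 0.7 (86 − 25); for 1 SD shifts it is small. These sizes rest on n = 20, alpha 0.05, normal data and assumed correlations.

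For pooled rows the documents support only the mechanism: type I error may be below, near or well above 5%. They do not support a claim that the planned analysis will produce false positives, since pooling is nowhere stated. What is established is that section 12 leaves the choice open. The text should be corrected before analysis.

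**What to change.** In section 12:

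1. Define the EtCO₂ value as the mean of the three readings in each subject-mask-EPAP cell, and name one pre-specified comfort summary per subject per mask. State alpha.
2. Compare EPAP levels within each mask, since the aim is an EPAP for each mask.
3. Replace Kruskal-Wallis with Friedman and Mann-Whitney with Wilcoxon signed-rank. Holm-adjust the six pairwise tests in each family. The adjustment is needed because the tests become paired; under the current plan, family-wise error in the case examined is at most 5.9%.
4. Alternatively, use a mixed model with fixed effects for mask, EPAP and period and random effects for subject, subject-by-mask and subject-by-EPAP (ordinal for comfort). This is preferable if any cells are missing, which the stopping rules in section 7 make possible.

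Before complete blocks are assumed, the section 3 statements on 15 minutes per mask and on four EPAP levels with a 5:00 reading must be reconciled. Section 3 randomises mask order but states no EPAP order; this should be stated too, because a common fixed order would leave EPAP inseparable from time on the mask under any analysis.

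**Cost.** The analysis change is wording only, with no new subjects or measurements. At zero correlation Friedman has less power than Kruskal-Wallis (34% against 42% at 0.6 SD). It needs complete blocks: with 4 of 20 subjects incomplete, power at ρ = 0.5 falls from 63% to about 50%. With Holm, detection of one given true 0.6 SD pair is 25 / 39 / 68 / 100% at ρ = 0.3 / 0.5 / 0.7 / 0.9, against 29 / 25 / 22 / 18% under the unadjusted plan, so there is a small loss at the lowest correlation and a gain elsewhere.

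### The EtCO₂-by-EPAP tests ignore the pairing within volunteers and the order of the EPAP levels, and no between-level difference, slope or confidence interval is planned

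*Combined protocol and SAP*

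**What the plan says.** Section 3 (Methods) describes the design: "This study will be a randomized crossover trial that will be conducted at Rush University". Every volunteer uses all four masks, and the pressures are fixed: "EPAP levels will be 0, 2, 4, & 5 while IPAP remains at 5 higher than EPAP". EtCO₂ is therefore recorded repeatedly on the same person at four increasing pressures, with steps of 2, 2 and 1 cm H₂O.

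Section 12 (Analysis) gives the measurement scale as "EPAP (ordinal), IPAP (ordinal) will be collected". EtCO₂ in relation to the "independent variable EPAP level will be analyzed by a Kruskal-Wallis test to determine if a significant difference exists". The follow-up is: "If a significant difference is found a Mann-Whitney U Test will be used to determine which EPAP levels significantly differ". The only summaries for EtCO₂ are these: "Means and Standard deviations will be calculated for aforementioned data". It is not said that they will be given by EPAP level.

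Section 4.2 gives the sample size as "20 healthy subjects", with no SD, effect size, alpha or power. Section 12 does not say whether the EPAP test is run for each mask or pooled over masks.

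**The concern.** Kruskal-Wallis and Mann-Whitney assume independent groups. With the same volunteers at every level, differences between volunteers enter the error term although they cancel in the comparison of interest. The tests also give the same answer if the four EPAP labels are shuffled, so the ordering that section 12 assigns to EPAP is not used. Friedman's test would restore the pairing but would still ignore the order.

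The aim is to find the EPAP needed to clear CO₂ with each mask. The plan defines no criterion for effective clearance, so statistical significance between levels is its only stated way of telling levels apart. Without an estimated difference and interval, a reader of the results cannot distinguish two levels that are alike from two levels that were compared with too little power. This is sharpest for 4 versus 5, the narrowest step.

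**Working it through.** **Inputs.** From the documents: 20 volunteers, EPAP 0, 2, 4, 5, Kruskal-Wallis then Mann-Whitney. The documents give no figures from which the 20 could be reproduced. Assumed: two-sided alpha 0.05; one mask, one EtCO₂ value per volunteer per level; the SDs and falls shown below.

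**1. Pairing and order, by simulation.** 4,000 trials per row, between-volunteer SD 4 mmHg, linear fall in EtCO₂ from EPAP 0 to 5. Power:

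| Within SD | Fall 0 to 5 | Kruskal-Wallis (as planned) | Friedman | Page trend | Within-volunteer slope |
|---|---|---|---|---|---|
| 2 mmHg | 1.5 mmHg | 0.3% | 42% | 59% | 69% |
| 2 mmHg | 2.0 mmHg | 2.4% | 68% | 83% | 91% |
| 1.5 mmHg | 1.5 mmHg | 0.3% | 67% | 83% | 92% |

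In the first row pairing adds about 42 points (0.3% to 42%) and order a further 17 (42% to 59%). Page against Friedman isolates order, since both use ranks; the slope also gains by not ranking.

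With other assumed SDs (3.5 between, 1.5 within) and a fall of 0.4 mmHg per cm H₂O (0.4 × 5 = 2.0 mmHg in all), the results are Kruskal-Wallis 5%, Friedman 92%, Page 98%. There order adds only 6 points.

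**2. How far the gain from order depends on shape.** A linear trend on scores 0, 2, 4, 5 uses a share r² of the available non-centrality, where r is the correlation between the true level means and the scores. The scores have mean 11/4 = 2.75 and sum of squares 7.5625 + 0.5625 + 1.5625 + 5.0625 = 14.75. At non-centrality 7.85 the 3-df unordered test has 64.5% power whatever the shape. The 1-df trend test has:

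| Shape of response | r² | 7.85 × r² | Trend power |
|---|---|---|---|
| Linear | 1.000 | 7.85 | 80% |
| Linear to 4, then flat | 0.963 | 7.56 | 78% |
| Step between 2 and 4 | 0.831 | 6.52 | 72% |
| Step between 0 and 2 | 0.684 | 5.37 | 64% |
| Step between 4 and 5 | 0.458 | 3.60 | 47% |

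For a linear response the unordered test needs non-centrality 10.90 for 80% power, against 7.85 for the trend test: 10.90/7.85 = 1.39, about 39% more information. For a non-monotone pattern (0, −3, −1, 0 mmHg; SD 4; independent values) trend power was about 5%, against 56% for Kruskal-Wallis.

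**3. Adjacent levels.** Take a linear fall large enough for 0 versus 5 to have 90% power, so z = 1.96 + 1.28 = 3.24. For a gap of g cm H₂O, z = 3.24 × g/5:

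- 2 versus 4 (g = 2): z = 1.296, power 25%.
- 4 versus 5 (g = 1): z = 0.648, power 10%.

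In the simulations of step 1 the paired Wilcoxon test for 4 versus 5 had 6.5% to 10% power, although EtCO₂ was still falling. With SDs 3.5 and 1.5 and a fall of 0.6 per cm H₂O, it had 22% against 0.1% for Mann-Whitney. At 0.8 per cm H₂O, 91% of simulated trials had a significant Kruskal-Wallis test with 4 versus 5 non-significant, although the fall was constant throughout. Pairing helps but does not remove the problem.

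**The case against.** Four points weigh on the other side.

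- **Direction.** A reader might infer that the protocol predicts a steady fall in EtCO₂ with pressure. It does not. The Introduction says that intentional leak affects clearance and that "the intentional leak level depends on the level of pressure", but it gives no direction and is commenting on studies of masks with intentional leaks. This trial uses a double-limb circuit, which the Introduction says usually runs without leak. A monotone response is plausible but not stated, so an unconditional claim that ignoring order loses power is not supported.
- **Aim.** The question is which pressure is needed. A slope averages over the shape and cannot name a level. Comparing levels, as the plan does, is closer to the aim. This stands, and is why a slope should not replace the level comparisons.
- **Plateau.** A reader might also infer that the plan treats non-significance as equivalence. No section says so; the risk is of misreading. Nor is it peculiar to 4 versus 5, since the 2-unit step has only 25% power in the same calculation.
- **Estimates and sequence.** Means and SDs are planned, so the results would not be p-values alone, but neither describes a within-volunteer difference. The text states no order for the EPAP levels (the procedure figure is not shown in the copy reviewed). If they always ascend, a slope on EPAP also absorbs any drift over time.

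None of this defends independent-group tests on repeated measures, or the absence of differences with intervals.

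**Conclusion.** The point holds in a limited form. The planned tests do not fit a design with repeated measures at ordered pressures, and the plan produces no estimate of how much EtCO₂ changes between levels. Ignoring the pairing is the main cost: under the assumed SDs the planned test falls from 42–68% power (Friedman) to between 0.3% and 2.4%. Ignoring the order is a second, conditional cost of about 15 to 17 points on the same data when the response is linear. It is nil for a step between 0 and 2 and reverses for a step between 4 and 5.

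All power figures rest on assumed SDs, effects and alpha, because the documents give none. The mismatch between tests and design does not depend on them. The low power for 4 versus 5 relative to 0 versus 5 follows from the spacing alone if the fall is linear. The change is worth making before analysis because it is cheap and bears directly on the trial's main question.

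**What to change.** In section 12, replace the Kruskal-Wallis and Mann-Whitney tests for EtCO₂ by EPAP with a within-volunteer analysis:

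1. Fit a mixed model for EtCO₂ with a volunteer effect and EPAP as a four-level factor, by mask.
2. For each mask, report the adjacent-level differences (0–2, 2–4, 4–5) with 95% confidence intervals.
3. Alongside these, not in their place, report an ordered estimate: the slope per cm H₂O on scores 0, 2, 4, 5 with its 95% confidence interval, or Page's test as the rank version. Keep the unordered paired comparison as well.
4. State that a non-significant difference between two levels, 4 versus 5 included, is not evidence of a plateau.
5. State the sequence in which EPAP levels are applied, so that readers can judge whether a trend might reflect time.

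The cost is wording and slightly more analysis work; no new data are needed. The trend estimate has little power for a non-monotone response or one confined to the last step, which is why the level comparisons stay.
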